4 SUBJECT SELECTION

4.1 Subject Recruitment

The study population will include adult male and female patients (n = 20), who underwent ITT from 2012 to present, are scheduled to undergo ITT in the future, or are clinically suspected to have adrenal insufficiency.

Eligible participants will be identified through a EMERSE and Data Direct search of individuals who have undergone ITT between 2012 and present, who have ITT ordered to be completed, or who have adrenal insufficiency listed as a clinical diagnosis. In addition, eligible participants will be recruited through physician referral and through **review of clinic schedules listing individuals scheduled for ITT.**

Patients will be called and offered participation by the study staff.

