12.4 STUDY DISCONTINUATION CRITERIA34
12.4.1 STOPPING RULES FOR SAFETY REASONS34
12.4.2 RULES FOR DISCONTINUATION OF A SUBJECT34
13 REFERENCES35

List of Tables

Table 1. Schedule of Activities.....22

PROTOCOL SYNOPSIS

Financial Sponsor: Corcept Therapeutics, Inc.
Name of Finished Product: Mifepristone (Korlym)
Study Title: Mifepristone Dynamic Testing for Diagnosis for Central Adrenal Insufficiency
Study Phase: Phase II
Primary Objective: Phase I of the study is to determine whether recruitment at our institution is sufficient for a study for mifepristone use as a diagnostic tool to diagnose central adrenal insufficiency and to generate data to inform a post-pilot study. Phase II of the study involves taking those recruited and having them complete the study to generate the data.
Study Design: Single-center pilot feasibility study of mifepristone to evaluate the recruitment of participants with the diagnosis of confirmed or suspected secondary adrenal insufficiency. Cortisol (secondary endpoint), ACTH and other steroid responses (exploratory endpoints) to mifepristone in participants with normal insulin tolerance testing (ITT) and participants with confirmed or suspected adrenal insufficiency will be analyzed. The study will test primarily for feasibility of recruitment (phase 1) and provide preliminary data for planning a post-pilot study (phase 2).
Study Population: Subjects with normal ITT and subjects with confirmed or suspected diagnosis of central adrenal insufficiency.
1. Criteria for Inclusion and Exclusion: Please see section 4.
Test Product; Dose; and Mode of Administration: Single dose of mifepristone 600mg, administered orally
Reference or Placebo Therapy; Dose; and Mode of Administration: None
Duration of Treatment: One day
Variables: Cortisol, ACTH

Statistical Methods:

- For the primary endpoint of recruitment actual recruitment will be compared to target recruitment (1 patient per 6 weeks). Actual and target recruitment per month will be plotted and visually compared. Recruitment of ≥ 26 participants and study completion and complete data on ≥ 22 patients will be a success regarding the primary endpoint.
- For the secondary endpoint the day 2 cortisol level will be compared to the maximal ITT cortisol level to determine if and to what degree there is a correlation between the two measurements.

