2.2 Endpoints

2.2.1 Primary Endpoint

The primary endpoint of this pilot feasibility study is actual study participant recruitment. Reaching the target recruitment rate of one patient every 6 weeks over a 36-month period will be regarded as successful in reaching the primary endpoint.

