7 ASSESSMENTS

7.1 Primary Endpoint Assessments

The primary endpoint of this pilot feasibility study is the rate of actual study participant recruitment. Reaching the target recruitment rate of one patient per 6 weeks over a 36-month period will be regarded as successfully in reaching the primary endpoint.

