9 DATA ANALYSIS/STATISTICAL METHODS

9.1 Sample Size Determination

This is a pilot-feasibility study with the primary endpoint of enrollment per month over a 36-month period. This study time frame was chosen due to the lack of any prior data regarding feasibility. Data required from this study will inform the planning of a post-pilot study.

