9.2 Data Analysis

9.2.1 *Analysis Populations*

As the primary endpoint recruitment will be analyzed as a primary endpoint. The cortisol response with mifepristone administration will be compared with the maximal ITT cortisol level in all patients as a secondary endpoint. In addition, the hormone levels of participants with normal ITT will be compared to those with confirmed diagnosis of central adrenal insufficiency. Data from this study will inform planning of a larger post-pilot study.

9.2.2 *Analysis of Primary Endpoint*

The primary endpoint of this pilot feasibility study is actual study participant recruitment. Reaching the target recruitment of one participant every 6 weeks over a 36-month period (target n=26) will be regarded successful in reaching the primary endpoint. We estimate an enrollment of 90% of patients in this study. This is in accordance with our prior experience in patients with rare diseases, who are often motivated regarding study participation. We estimate a total of 85% of patients with complete data as we only anticipate minimal study drop out due to side effects of the drug or non-analyzable specimens. Study recruitment will be plotted over time and actual and target recruitment will be visually compared. We will regard a total of 22 patients as a target in meeting the primary endpoint.

9.2.3 *Analysis of Secondary Endpoints*

The secondary data point is day 2 cortisol and ACTH response to mifepristone administration. The day 2 cortisol level will be compared to the maximal ITT cortisol level to determine if and to what degree there is a correlation between the two measurements. In addition, a receiver operating characteristic (ROC) curve will be created with the day 2 cortisol level as the variable, and the ITT result as the “gold standard” test for adrenal insufficiency, to analyze the performance of cortisol as a diagnostic test. The cortisol and ACTH values in participants with normal ITT will be compared to those with confirmed diagnosis of central adrenal insufficiency, using a

t-test to determine whether there is statistically significant difference between the two populations.

9.2.4 *Analysis of Secondary Endpoints*

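### The study size of 20 in section 4.1 is below both primary-endpoint thresholds (26 recruited, 22 complete), and the success rule differs between sections

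*Combined protocol and SAP*

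**What the plan says.** The combined protocol and SAP gives a study size or a success rule for the primary endpoint in six places.

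- **Section 4.1 (Subject Recruitment):** "The study population will include adult male and female patients (n = 20"). It does not say whether 20 means approached, enrolled or complete.
- **Synopsis, Statistical Methods:** "Recruitment of ≥ 26 participants and study completion and complete data on ≥ 22 patients will be a success regarding the primary endpoint". This is a joint rule, and both numbers are minimums.
- **Section 2.2.1:** "Reaching the target recruitment rate of one patient every 6 weeks over a 36-month period will be regarded as successful". There is no completion condition.
- **Section 7.1:** the same rate-only rule, "one patient per 6 weeks over a 36-month period will be regarded as successfully in reaching the primary endpoint".
- **Section 9.1 (Sample Size Determination):** "This is a pilot-feasibility study with the primary endpoint of enrollment per month over a 36-month period". It gives no number of participants.
- **Section 9.2.2:** the recruitment target is restated as "target n=26) will be regarded successful in reaching the primary endpoint". Two assumptions follow: "We estimate an enrollment of 90% of patients in this study" and "We estimate a total of 85% of patients with complete data". The section ends by naming 22 patients as a target for the primary endpoint. It does not say whether these are recruited or complete, or whether the 22 is needed in addition to the 26.

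**The concern.** Recruitment is the primary endpoint of this pilot, so the count and the success rule are its primary analysis. Two things go wrong.

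First, the study size in section 4.1 is smaller than either number that defines success. A team that treated 20 as the enrolment total would follow that section and could not meet the synopsis rule.

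Second, the rule itself changes between sections. The synopsis requires completion; sections 2.2.1 and 7.1 do not. One set of results can then be reported as a success or a failure, and the choice could be made once the counts are known.

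A smaller gap sits beside these: the 90% enrolment assumption in section 9.2.2 has no stated denominator, so it cannot be linked to 20, 22 or 26.

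**Working it through.** **Inputs.** One patient per 6 weeks for 36 months (2.2.1, 7.1, 9.2.2); 85% with complete data and 90% enrolment (9.2.2); minimums of 26 and 22 (synopsis); n = 20 (4.1).

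**The plan's own figures.**
- 36 months x 365.25 / 12 / 7 = 156.5 weeks.
- Recruitment target: 156.5 / 6 = 26.1, so 26. This reproduces.
- Complete data: 26 x 0.85 = 22.1, so 22. This reproduces.

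So 26 and 22 form a coherent pair of recruited and complete.

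**Can 20 be reached from the same inputs?**
- As a recruitment target: no. Even counting each month as four weeks gives 144 / 6 = 24.
- 26 x 0.90 x 0.85 = 19.9, and 22 x 0.90 = 19.8. Both are close to 20, but the plan writes neither, and either would contradict its own 22, which is what the 85% alone gives.

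**Size of the gap.**
- 20 as enrolled: 26 - 20 = 6 short, 20 / 26 = 77% of target. Over 36 months that is 156.5 / 20 = 7.8 weeks per patient. At the target pace, enrolment would end after 20 x 6 = 120 weeks, about 27.6 months. Expected complete: 20 x 0.85 = 17.
- 20 as complete: 22 - 20 = 2 short. It implies 20 / 26 = 77% completeness instead of 85%, or 20 / 0.85 = 23.5 enrolled instead of 26.

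**The rules applied to the same result.**

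| Result | 2.2.1 and 7.1 | Synopsis |
|---|---|---|
| 26 recruited, 22 complete | success | success |
| 26 recruited, 21 complete | success | failure |

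**How often the split would occur.** With exactly 26 recruited, the two rules disagree whenever 21 or fewer are complete. Treating participants as independent (my assumption), the probability is P(Bin(26, p) ≤ 21):

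| Completeness p | Probability of a split |
|---|---|
| 0.80 | 0.617 |
| 0.85 (the plan's figure) | 0.350 |
| 0.90 | 0.112 |

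At p = 0.85 the expected number complete, 22.1, lies almost on the threshold. The probability falls if more than 26 are recruited: 0.210 with 27, 0.115 with 28 and 0.028 with 30.

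**The case against.** The strongest reply is that nothing makes 20 a cap. It is a parenthesis in a descriptive sentence, section 3 has all eligible adults approached, and no text stops enrolment at 20. That is fair: the claim that the thresholds cannot be reached holds only if 20 is total enrolment. Read as the number complete it still falls below 22, so the conflict stays.

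A second reply is that the 22 in section 9.2.2 plainly means complete data, since it follows the 85% sentence and the synopsis says so. I accept that as the natural reading. An example with 24 recruited and 22 complete, which passes only if the last sentence of 9.2.2 is read alone, is therefore weak and I do not rely on it. The split at 26 recruited and 21 complete does not depend on that reading, because sections 2.2.1 and 7.1 carry no completion condition at all.

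Third, the 35% applies to exactly 26 recruited and shrinks quickly above that. This stands: it is not an overall probability that the trial meets the conflict.

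Fourth, a feasibility count has no test or error rate, and readers given both counts could apply either rule. This limits the harm, but the plan commits to declaring success or failure and should fix in advance how.

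Finally, the plan's arithmetic also fits a rule of 26 alone with 22 as the expected yield, so it does not by itself choose the joint rule. This also stands; the choice is the sponsor's.

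**Conclusion.** The concern holds and must be fixed. The stated study size of 20 lies below both minimums in the synopsis: by 6 if it counts enrolment, by 2 if it counts complete data. Independently of that, the synopsis requires completion while 2.2.1 and 7.1 do not, so a result of 26 recruited and 21 complete is scored both ways, and no section is given precedence.

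The contradiction itself needs no assumption. The 0.35 rests on exactly 26 recruited, 85% completeness and independence between participants. The arithmetic behind 26 and 22 is sound; the fault is inconsistency between sections. The undefined 90% is missing detail and would not carry the finding alone.

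**What to change.** 1. Have the sponsor state what 20 counts in section 4.1. Either replace it with the enrolment figure the success rule needs (26), or define it and reconcile it with 22.
2. Put one success rule, with its denominators, in the synopsis and in sections 2.2.1, 7.1 and 9.2.2. The joint rule in the synopsis (at least 26 recruited and at least 22 with complete data) fits the plan's arithmetic. If the sponsor prefers recruitment alone, 22 should be labelled throughout as an expected yield.
3. If the joint rule is kept, join the two numbers in section 9.2.2 with 'and', and say that the 22 are patients with complete data.
4. Give the same enrolment number in section 9.1.
5. Say what the 90% applies to. Delete it only once its link to the 20, if any, has been settled.

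**Cost.** Wording in six places through one IRB-reviewed amendment, with no change to visits or data collection. The joint rule makes success harder to claim than 2.2.1 and 7.1 do now: with 26 enrolled and 85% completeness, the chance of at least 22 complete is 1 - 0.350 = 0.65. A sponsor who adopts it should decide knowingly whether enrolling exactly 26 is enough.

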4.1.1 Inclusion Criteria

Adult (ages ≥ 18 years of age) male and female subjects who:

1. Completed ITT at University of Michigan from 2012 to present.
OR
2. Are scheduled to complete ITT.
OR
3. Are clinically suspected to have adrenal insufficiency but have not undergone ITT.

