1 INTRODUCTION

1.1 Indication

Central adrenal insufficiency (CAI) is the inadequate production of cortisol in the setting of physiologic stress. In contrast to primary adrenal insufficiency, CAI is due to pituitary or hypothalamic dysfunction. Today, CAI has a prevalence of roughly 150-280 per million.ⁱ The most common cause of CAI is administration of exogenous glucocorticoids. Other common pharmacologic causes of CAI include synthetic progestins and opiates, which can suppress the hypothalamic-pituitary-adrenal (HPA) axis. Primary pituitary pathologies include tumors, congenital or developmental causes, and hypophysitis. Brain trauma, radiation, and granulomatous diseases can also affect the neuroendocrine components of the (HPA) axis.

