2.2.2 Secondary Endpoint

The secondary endpoint is the correlation between the peak cortisol measured in ITT (the gold standard) and the cortisol measured the day after mifepristone administration. We will assess whether there is a strong relationship between ITT peak cortisol and the cortisol measured after mifepristone administration. We hypothesize that the Pearson's correlation coefficient (r) for this correlation will be > 0.7 . The results of the ITT will be regarded as the gold standard in the diagnosis of secondary adrenal insufficiency. As the true cut-off for diagnosis of adrenal insufficiency using post-mifepristone cortisol is unknown we will analyze the data using ROC c-statistics for different cut-offs.

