3 STUDY DESIGN

This will be a single-center trial of mifepristone to evaluate the ACTH and cortisol response to mifepristone in participants without history of adrenal insufficiency and participants with confirmed or suspected adrenal insufficiency. All adult participants who have undergone ITT from 2012 to present, are scheduled to undergo ITT in the future, or are clinically suspected to have adrenal insufficiency, will be approached for this study. There will be at least a one-week interval between ITT and mifepristone testing.

Subjects who meet inclusion criteria and agree to participation will undergo the study conducted over two days: baseline hormone labs will be obtained on the morning of day 1. A single dose of 600mg mifepristone is to be orally taken at 10PM on day 1. Participants will then return for repeat lab work on day 2.

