4.1.2 Exclusion Criteria

1. Female patients who are of child-bearing potential (defined as a sexually mature woman who has not undergone hysterectomy, bilateral oophorectomy bilateral salpingectomy or bilateral tubal ligation/occlusion, at least 12 weeks prior to screening, or who has not been naturally postmenopausal for at least 24 consecutive months prior to study enrollment) and not using non-hormonal contraception.

2. Female patients not willing to use non-hormonal contraception for one month following treatment.
3. Women who are breast feeding.
4. Female patients who have a positive pregnancy test. [SEP]
5. Female patients with unexplained vaginal bleeding or history of endometrial hyperplasia with atypia or carcinoma. [SEP]
6. Patients with an existing diagnosis of adrenal insufficiency who are on any glucocorticoid replacement other than oral hydrocortisone or prednisone.
7. Patients with hypokalemia < 3.5 mEq/L on lab work completed on Day 1 or obtained within 3 months prior to Day 1.
8. Patients with AST or ALT greater than 3 times the upper limit of normal on lab work completed on Day 1 or obtained within 3 months prior to Day 1.
9. Hypertensive patients with uncontrolled blood pressure defined as SBP > 180 and/or DBP > 100 .
10. Patients on medications that are CYP3A substrates with narrow therapeutic ranges, such as cyclosporine, dihydroergotamine, ergotamine, fentanyl, pimozide, quinidine, sirolimus, and tacrolimus.
11. Patients on medications that are strong CYP3A inhibitors (such as itraconazole, nefazodone, ritonavir, nelfinavir, indinavir, atazanavir, amprenavir, fosamprenavir, boceprevir, clarithromycin, conivaptan, lopinavir, mibefradil, posaconazole, saquinavir, telaprevir, telithromycin, and voriconazole) or inducers (such as rifampin, rifabutin, rifapentine, phenobarbital, phenytoin, carbamazepine, St. John's wort).
12. Patients taking other medications metabolized by CYP3A, such as simvastatin, lovastatin.
13. Patients who are not euthyroid as judged by the investigator.
14. Patients with history of hypersensitivity to mifepristone or the tablet components
15. Patients who have a history of QT prolongation and patients with any recent abnormal ECG.

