6 STUDY PROCEDURES- SEE THE SCHEDULE OF ACTIVITIES

6.1 Screening Visit

Potential subjects will be contacted over the phone to review their past medical history and current medications. If the potential participant is a woman of childbearing potential, she will be asked to take an at-home urine pregnancy test or come in for a urine or serum pregnancy test one week prior to visit 1. If they do not meet any pre-screening exclusion criteria, they will present for Day 1 of the study and complete screening labs on this day.

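### The reference ITT may date back to 2012 with no maximum age, and no rule asks whether adrenal-axis status has changed since, so disease change can count as test error in the secondary analyses

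*Combined protocol and SAP*

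**What the plan says.** Section 4.1.1 gives three routes of entry. The first is "Completed ITT at University of Michigan from 2012 to present". Section 3 adds the only rule on timing: "There will be at least a one-week interval between ITT and mifepristone testing". Footnote a of the Schedule of Activities repeats it. No section sets an upper limit or asks for a repeat ITT.

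Section 2.2.2 gives the ITT its role: "The results of the ITT will be regarded as the gold standard in the diagnosis of secondary adrenal insufficiency". It also states the expected strength of agreement: "We hypothesize that the Pearson's correlation coefficient (r) for this correlation will be > 0.7". Section 9.2.1 applies the comparison without restriction: "The cortisol response with mifepristone administration will be compared with the maximal ITT cortisol level in all patients as a secondary endpoint". Section 9.2.3 uses the ITT result as the reference for the ROC curve. Sections 9.2.3 and 9.2.4 compare participants with a normal ITT with those who have a confirmed diagnosis of central adrenal insufficiency.

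Section 1.1 says of causes: "The most common cause of CAI is administration of exogenous glucocorticoids". It goes on to name progestins, opiates, tumours, brain trauma and radiation.

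There is some screening. Section 6.1 says: "Potential subjects will be contacted over the phone to review their past medical history and current medications". History is taken again on Day 1, and baseline cortisol and ACTH are drawn. The one exclusion on glucocorticoids in section 4.1.2 is "Patients with an existing diagnosis of adrenal insufficiency who are on any glucocorticoid replacement other than oral hydrocortisone or prednisone".

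**The concern.** The secondary question is whether cortisol on the morning after mifepristone tracks the ITT. That comparison assumes both tests describe the same adrenal axis. Several causes in section 1.1 are drug exposures, which begin and end. Others, such as irradiation or trauma, can come after a normal ITT. Someone who failed an ITT while on a suppressing drug may since have recovered; someone who passed may since have lost function.

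In either case a mifepristone result that is right about present status is scored as a disagreement. If neither the ITT date nor the intervening events enter the analysis, disagreement from disease change cannot be told apart from failure of the test. The output meant to inform a post-pilot study would then understate the test, by an amount nobody could estimate afterwards.

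**Working it through.** **The plan's own figures.** 36 months is 36 × 365.25 / 12 / 7 = 156.5 weeks, and 156.5 / 6 = 26.1, which gives the target of 26. Then 26 × 0.85 = 22.1, which gives 22 with complete data. Both reproduce (section 9.2.2). No sample-size calculation is given for r > 0.7. Below I take n = 22 and assume that every completer has an ITT.

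**Is there an upper limit or an ITT-linked rule?**
- Sections 3, 4.1 and 4.1.1 and the Schedule of Activities give a 2012 start and a one-week minimum, and nothing else on timing.
- The phone review and the Day 1 history are general. No eligibility criterion or analysis rule uses them to question the ITT.
- The glucocorticoid exclusion covers only people already diagnosed with adrenal insufficiency, and only the type of replacement.
- Day 1 cortisol and ACTH are not used to confirm that the ITT result still holds.

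**Correlation.** Assumptions: true r between same-time measurements is 0.80; a fraction f of ITT peaks is unrelated to present status but has the same mean and variance as the rest. Then expected r = (1 − f) × 0.80. The last column is a simulation with normal data (n = 22, 40,000 runs).

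| f | Expected r | P(observed r > 0.7) |
|---|---|---|
| 0 | 0.80 | 0.87 |
| 10% | 0.72 | 0.62 |
| 20% | 0.64 | 0.41 |
| 30% | 0.56 | 0.24 |

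Expected r reaches 0.70 at f = 1 − 0.70/0.80 = 12.5%, and 0.125 × 22 = 2.75, or about 3 participants.

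**Precision.** The Fisher-z 95% interval is tanh(atanh(r) ± 1.96/√(22 − 3)), a half-width of 0.450 on the z scale. An observed r of 0.70 gives 0.40 to 0.87. An observed r of 0.64 gives 0.30 to 0.84, which still contains 0.70 and 0.80.

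**ROC.** Assumptions: true AUC A = 0.95; Day 2 cortisol depends only on present status; a share p of ITT-abnormal participants has recovered and a share q of ITT-normal participants has lost function. Then

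AUC_obs = (1 − p)(1 − q)A + 0.5[(1 − p)q + p(1 − q)] + pq(1 − A).

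- p = 10%, q = 5%: 0.81225 + 0.07 + 0.00025 = 0.8825, about 0.88.
- p = 20%, q = 10%: 0.684 + 0.13 + 0.001 = 0.815, about 0.82.
- p = 30%, q = 10%: 0.5985 + 0.17 + 0.0015 = 0.77.

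The two models differ: the first makes an old peak uninformative, the second reverses status. f, p and q, like the true r and AUC, are assumed, because the documents give none of them.

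**The case against.** The strongest reply is that this is a feasibility pilot in a rare diagnosis. Recruitment is the primary endpoint, and a wide ITT window serves it. No go/no-go rule hangs on r or the AUC; r > 0.7 is an expectation. All of that stands. It limits how much is at stake and is the reason to leave eligibility alone, but it does not make an outdated reference valid.

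A reader might infer more than the documents support:

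- **That nothing is checked.** History, medications and Day 1 hormones are all collected. What is missing is a rule linking them to the ITT.
- **That r > 0.7 will fail at 20% outdated ITTs.** Only the expected value falls below 0.7. Under the assumptions above, the observed r still exceeds 0.7 with probability 0.41.
- **That every analysis covers all patients under the old ITT label.** Section 9.2.1 uses that scope for the comparison with the ITT peak. In the t-tests, the insufficiency group is defined by a confirmed diagnosis, which is not stated to rest on the old ITT; the problem enters there through the normal-ITT group.
- **That reference tests will be many years old.** The documents give no recruitment start date and no distribution of ITT dates. The June 2017 Investigator's Brochure cited in section 8.1 dates a reference, not enrolment. Participants with a scheduled ITT need not have an old test, although their interval has no upper limit either.
- **That the 3-month limit on screening chemistry sets a precedent.** It supports the safety exclusions on potassium and liver enzymes and says little about the reference test.
- **That anyone who started a glucocorticoid after the ITT should be left out.** A participant diagnosed by a failed ITT would be expected to start replacement, and section 6.2.3 provides for such participants. Leaving them out would selectively remove ITT-abnormal participants and narrow the cortisol range behind r.

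**Conclusion.** The gap in the text is certain: the reference test has a minimum interval but no maximum, and no rule asks whether it still describes the participant. Followed as written, a change in axis status counts as test error in the correlation and ROC and biases both towards no agreement. The t-tests are affected through the normal-ITT group. The recruitment endpoint and the targets of 26 and 22 are not affected.

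The size is unknown. Under the stated assumptions, 10% to 30% outdated ITTs lower an r of 0.80 to between 0.72 and 0.56, and the chosen recovery and loss rates lower an AUC of 0.95 to between 0.88 and 0.77. Partial change would do less. With about 22 pairs, around three outdated peaks are enough to bring expected r down to 0.70. This is a worthwhile, inexpensive improvement to the secondary analyses, not a flaw that defeats the study.

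**What to change.** Leave eligibility and the recruitment targets as they are.

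1. Record the date of each ITT. From the chart, and before Day 2 cortisol is seen, record any axis-altering event between the ITT and mifepristone testing: pituitary surgery, cranial irradiation, head trauma, or start or stop of an opiate, progestin or glucocorticoid.
2. State that glucocorticoid replacement started because of the ITT result or an adrenal insufficiency diagnosis is not an event.
3. In sections 9.2.1 and 9.2.3, keep the all-patients analysis. Beside it, pre-specify the correlation, the ROC and the ITT-based t-tests in (a) participants without such an event and (b) participants whose ITT falls within a pre-stated interval, for example 12 months.
4. Report the distribution of the ITT-to-test interval.

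The rules need to be fixed in advance, because exclusions chosen after discordant results are known would themselves be biased. The cost is protocol wording and some chart review, with no new procedure. The restricted analyses will have fewer pairs and so wider intervals, and should be read beside the all-patients result.
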